13.2. FDA Table for Laboratory Grading

Table 12-2 Laboratory Abnormalities

Serum ^a	Mild (Grade 1)	Moderate (Grade 2)	Severe (Grade 3)	Potentially Life Threatening (Grade 4) ^b
Sodium – hyponatremia (mEq/L)	132-134	130-131	125-129	< 125
Sodium – hypernatremia (mEq/L)	144-145	146-147	148-150	> 150
Potassium – hyperkalemia (mEq/L)	5.1-5.2	5.3-5.4	5.5-5.6	> 5.6
Potassium – hypokalemia (mEq/L)	3.5-3.6	3.3-3.4	3.1-3.2	< 3.1
Glucose – hyperglycemia Random(mg/dL)	110-125	126-200	> 200	Insulin requirements or hyperosmolar coma
Blood Urea Nitrogen (mg/dL)	23-26	27-31	> 31	Requires dialysis
Creatinine (mg/dL)*	1.5-1.7	1.8-2.0	2.1-2.5	> 2.5 or requires dialysis
Calcium – hypocalcemia (mg/dL)	8.0-8.4	7.5-7.9	7.0-7.4	< 7.0
Calcium – hypercalcemia (mg/dL)	10.5-11.0	11.1-11.5	11.6-12.0	> 12.0
Albumin – hypoalbuminemia (g/dL)	2.8-3.1	2.5-2.7	< 2.5	--
Total Protein – hypoproteinemia (g/dL)	5.5-6.0	5.0-5.4	<5.0	--
Liver Function Tests –ALT, AST increase by factor*	1.1-2.5 × ULN	2.6-5.0 × ULN	5.1-10 × ULN	> 10 × ULN
Bilirubin – when accompanied by any increase in liver function test increase by factor*	1.1-1.25 × ULN	1.26-1.5 × ULN	1.51-1.75 × ULN	> 1.75 × ULN
Bilirubin – when liver function test is normal; increase by factor*	1.1-1.5 × ULN	1.6-2.0 × ULN	2.0-3.0 × ULN	> 3.0 × ULN
Hematology ^a	Mild (Grade 1)	Moderate (Grade 2)	Severe (Grade 3)	Potentially Life Threatening (Grade 4) ^b
Hemoglobin (Female)(gm/dL)*	11.0-12.0	9.5-10.9	8.0-9.4	< 8.0
Hemoglobin (Female) change from baseline value (gm/dL)	Any decrease - 1.5	1.6-2.0	2.1-5.0	> 5.0
Hemoglobin (Male)(gm/dL)*	12.5-13.5	10.5-12.4	8.5-10.4	< 8.5
Hemoglobin (Male) change from baseline value (gm/dL)	Any decrease - 1.5	1.6-2.0	2.1-5.0	> 5.0
WBC Increase(cell/mm ³)*	10,800-15,000	15,001-20,000	20,001-25,000	> 25,000
WBC Decrease (cell/mm ³)*	2,500-3,500	1,500-2,499	1,000-1,499	< 1,000
Platelets Decreased - cell/mm ³ *	125,000 – 140,000	100,000 – 124,000	25,000 – 99,000	< 25,000
Prothrombin time – increase by factor*	1.0-1.10 × ULN	1.11-1.20 × ULN	1.21-1.25 × ULN	> 1.25 × ULN

partial thromboplastin time – increase by factor *	1.0-1.2 × ULN	1.21-1.4 × ULN	1.41-1.5 × ULN	> 1.5 × ULN
---	---------------	----------------	----------------	-------------

Abbreviations: ALT, alanine aminotransferase; AST, aspartate aminotransferase; ULN, upper limit of normal; WBC, white blood cell.

*Screening labs with toxicity scores greater than 1 are exclusion criteria for the full cohort only (greyed line items).

All safety labs listed in Table 13-2 with a toxicity score greater than 1 are exclusion criteria for the safety cohort.

^a The laboratory values provided in the tables serve as guidelines and are dependent upon institutional normal parameters. Institutional normal reference ranges should be provided to demonstrate that they are appropriate.

^b The clinical signs or symptoms associated with laboratory abnormalities might result in characterization of the laboratory abnormalities as Potentially Life Threatening (Grade 4). For example, a low sodium value that falls within a grade 3 parameter (125-129 mE/L) should be recorded as a grade 4 hyponatremia event if the subject had a new seizure associated with the low sodium value.

Source: DHHS 2007

13.3. FDA Table for Vital Sign Grading – Vital Sign Abnormality

Table 12-3 Vital Sign Abnormality

Vital Signs ^a	Mild (Grade 1)	Moderate (Grade 2)	Severe (Grade 3)	Potentially Life Threatening (Grade 4)
Fever (°F) ^b	100.4 – 101.1	101.2 – 102.0	102.1 – 104	>104
Tachycardia (beats per minute)	101 – 115	116 – 130	>130	Emergency room visit or hospitalization for arrhythmia
Bradycardia (beats per minute) ^c	50 – 54	45 – 49	<45	ER visit or hospitalization for arrhythmia
Hypertension (systolic) (mm Hg)	141 – 150	151 – 155	>155	ER visit or hospitalization for malignant hypertension
Hypertension (diastolic) (mm Hg)	91 – 95	96 – 100	>100	ER visit or hospitalization for malignant hypertension
Hypotension (systolic) (mm Hg)	85 – 89	80 – 84	<80	ER visit or hospitalization for hypotensive shock

Note: Grade 0 will be the classification if the observation is less than a Grade 1. Respiratory rate was removed from the FDA table for vital sign grading as this is not a parameter being measured in this study.

- a. Subject should be at rest for all vital sign measurements.
- b. Oral temperature; no recent hot or cold beverages or smoking.
- c. When resting heart rate is between 60 to 100 beats per minute. Use clinical judgement when characterizing bradycardia among some healthy subject populations, for example, conditioned athletes.

Source: [DHHS 2007](#).

13.4. Guideline of Missing Date Imputation for Safety Analysis

Impute Missing Adverse Events/ Prior or Concomitant Medications

A. Incomplete Start Date:

If the stop date is not missing, and the imputed start date is after the stop date, the start date will be imputed by the stop date.

Missing day and month

- If the year is the **same** as the year of the first dosing date, then the day and month of the first dosing date will be assigned to the missing fields.
- If the year is **prior to** the year of first dosing date, then December 31 will be assigned to the missing fields.
- If the year is **after** the year of first dosing, then January 1 will be assigned to the missing fields.

Missing day only

- If the month and year are the **same** as the year and month of first dosing date, then the first dosing date will be assigned to the missing day.
- If either the year of the partial date is **before** the year of the first dosing date or the years of the partial date and the first dosing date are the same but the month of partial date is **before** the month of the first dosing date, then the last day of the month will be assigned to the missing day.
- If either the year of the partial date is **after** the year of the first dosing date or the years of the partial date and the first dose date are the same but the month of partial date is **after** the month of the first dosing date, then the first day of the month will be assigned to the missing day.
- If the stop date is not missing, and the imputed start date is after the stop date, the start date will be imputed by the stop date, i.e. set to the stop date.

Missing day, month, and year

- No imputation is needed; the corresponding AE will be included as TEAE provided the end date of the AE is after the first dose date or the end date is also missing.

B. Incomplete End Date:

If the imputed stop date is before the start date, then the imputed stop date will be equal to the start date.

Missing day and month

- If the year of the incomplete stop date is the **same** as the year of the last dosing date, then the day and month of the last dosing date will be assigned to the missing fields.
- If the year of the incomplete stop date is **prior to** the year of the last dosing date, then December 31 will be assigned to the missing fields.

- If the year of the incomplete stop date is **prior to** the year of the last dosing date but is the same as the year of the first dosing date, then the first dosing date will be assigned to the missing date.
- If the year of the incomplete stop date is **after** the year of the last dosing date, then January 1 will be assigned to the missing fields.

Missing day only

- If the month and year of the incomplete stop date are the **same** as the month and year of the last dosing date, then the day of the last dosing date will be assigned to the missing day.
- If either the year of the partial date is **not equal to** the year of the last dosing date or the years of the partial date and the last dosing date are the same but the month of partial date is **not equal to** the month of the last dosing date, then the last day of the month will be assigned to the missing day.

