4.6. Handling of Missing Data

Data will be presented in the listings as reported. For summaries and analysis, the following conventions apply.

Immunogenicity Data

No Imputation methods will be used for missing immunogenicity data and all analyses will be based on complete records only.

Any pertussis antigen specific antibody titer (PT, FHA, PRN, FIM 2/3, or BPZE1 whole cell extract) from either serum or nasal mucosal sample that is below the minimal limit of assay detection will be imputed with a value equal to half of the minimal limit of assay detection of the antigen specific antibody titer.

Adverse Event Data

Missing date will be imputed as described in [Appendix 13.4](#). Missing information regarding ‘relationship to study vaccine’ or ‘severity’ will be imputed as related to study vaccine and severe, as the worst-case scenario.

Prior/Concomitant Medication Data

Missing date will be imputed as described in [Appendix 13.4](#).

5. Subject Disposition

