9.2.2. Severity of Adverse Event

TEAEs will be rated as Mild, Moderate, or Severe based on the following criteria:

- Mild: These events require minimal or no treatment and do not interfere with the subject's daily activities.
- Moderate: These events result in a low level of inconvenience or concern with the therapeutic measures. Moderate events may cause some interference with normal functioning.
- Severe: These events interrupt a subject's usual daily activity and may require systemic drug therapy or other treatment. Severe events are usually incapacitating.

If a subject reports multiple occurrence of a specific event, the subject will be counted only once by the maximum severity. If the severity is missing for one or more of the occurrences, the maximum severity of the remaining occurrences will be used.

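### SAP 13.4 imputes adverse event dates as if there were one dose: partial start dates ignore the boost, and partial stop dates can become a dosing date or have two answers

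*SAP*

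**What the plan says.** SAP 4.6 sends missing AE dates to Appendix 13.4.

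**Start dates.** Every rule compares the partial date with the first dosing date. With the day missing in a month after the first-dose month, "then the first day of the month will be assigned to the missing day". With day and month missing, a date in the first-dose year takes the prime date, and a date in a later year takes 1 January. The boost date is never used.

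**Stop dates.** With the day missing in the month and year of the last dose, "then the day of the last dosing date will be assigned to the missing day". In any other month the stop goes to month end. With day and month missing in the year of the last dose, "then the day and month of the last dosing date will be assigned to the missing fields". A year-only stop before the year of the last dose meets two consecutive bullets. The first reads "the year of the last dosing date, then December 31 will be assigned to the missing fields". The second adds the condition that the stop year "is the same as the year of the first dosing date, then the first dosing date will be assigned to the missing date". A floor applies throughout: "If the imputed stop date is before the start date, then the imputed stop date will be equal to the start date".

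**Where the dates are used.** SAP 4.4 ends the prime period the day before the boost, and SAP 9.2 tabulates AEs for Days 1 to 84, 85 to 113, and 114 onward. SAP 9.1 summarises Duration Through Resolution of solicited events as the diary days plus the days beyond 7 captured as an AE.

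**The concern.** An imputed start date decides whether an AE is tabulated under the prime or the boost. Rules that ignore the boost will put some boost AEs in the wrong table. Arm C receives Boostrix first and BPZE1 second, so a BPZE1 event moved to the prime period is shown under the comparator.

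Stop dates matter because duration of solicited events is part of a primary safety endpoint (SAP 3.2.1.2). A reaction is entered as an AE only if it extends beyond 7 days, and it keeps its original start date. A rule that can place its stop on the day of vaccination contradicts the reason the AE record exists.

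Where two bullets cover the same date, two programmers following the SAP exactly can get different results.

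**Working it through.** The plan states no figure to reproduce. The check applies the 13.4 rules as written.

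**Inputs.** The boost is 84 days after the prime (Day 85), or up to 94 days with the +10-day window in the schedule of events. The diary covers the vaccination day and 7 further days. Assumptions for the shares: prime dates uniform over a calendar year; post-boost AE starts uniform over days 0 to 28 after the boost; persistent reactions start on the vaccination day and stop 8 to 27 days later. All shares are conditional on the date being partial.

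**1. Start dates.** Prime 27 Jan 2020, boost 27 Jan + 84 days = 20 Apr 2020, true AE start 22 Apr.
- Day missing: imputed 1 Apr, before the boost, so prime period.
- Day and month missing: imputed 27 Jan, so prime period.

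An event is not moved if the boost was on the 1st, or if the event falls in a later month (day missing) or a later year (day and month missing) than the boost. Under the assumptions, about 51% of post-boost AEs with the day missing and about 96% with day and month missing are moved. Gaps of 84 to 94 days give the same result.

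The 1st of the boost month lies 1 to 30 days before a boost given on the 2nd to the 31st. For a Day 85 boost that is Day 55 to Day 84. SAP 9.2 records only related AEs and SAEs on Days 30 to 84, so an unrelated non-serious boost AE can land where such events are not collected.

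Effect by arm:

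| Arm | Event moved from | Counted under |
|---|---|---|
| A | BPZE1 boost | BPZE1 prime |
| B | placebo boost | BPZE1 prime |
| C | BPZE1 boost | Boostrix prime |
| D | placebo boost | Boostrix prime |

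**2. Stop dates.** *Post-boost:* boost and onset 6 Apr 2020, true stop 16 Apr (11 days), stop day missing. The imputed stop is 6 Apr, the onset day. The diary for the same reaction runs from 6 to 13 Apr, and SAP 9.1 counts those days, so the AE record and the diary disagree.

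*Post-prime:* prime and onset 27 Jan 2020, true stop 7 Feb (12 days), stop given only as 2020. The imputed stop is the boost date, 20 Apr, giving 85 days.

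From the imputed dates alone, over all prime dates in 2020 with an 84-day gap:

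| Persistent reaction after | Partial stop | Shortened | Lengthened | Mean shift |
|---|---|---|---|---|
| Boost | day missing | 42% | 58% | +5 days |
| Boost | year only | 99.7% | 0% | -17 days |
| Prime | day missing | 0% | 97% | +15 days |
| Prime | year only, 31 December bullet | 0% | 99.7% | +60 days |
| Prime | year only, first-dose bullet | 18% | 82% | +51 days |

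**3. Conflicting bullets.** Prime 18 Nov 2019, boost 18 Nov + 84 days = 10 Feb 2020, stop given only as 2019. One bullet gives 31 Dec 2019 and the next gives 18 Nov 2019, which is 43 days apart. Prime and boost fall in different years for 84/365 = 23% of prime dates (94/365 = 26% at a 94-day gap).

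**The case against.** The strongest objection concerns reach. Protocol 6.3.5.5 requires start and stop dates for every AE, and post-boost visits fall on Days 92, 96 and 113, so partial dates may be few. Solicited events come from the diary, are summarised relative to the most recent vaccination, and normally have a known start, so start-date imputation should hardly touch them. SAP 9.2 names only start dates for unsolicited AEs, and no duration of unsolicited AEs is summarised. Partial stop dates therefore reach a summary only through Duration Through Resolution, for reactions lasting beyond 7 days. Listings show dates as reported. All of this stands and limits the weight of the point.

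The conflicting bullets could be read as a general rule followed by an exception. The SAP does not say so, and the exception would set a stop date to the prime date.

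A reader might also infer that the rules shorten durations in general and that the errors favour the vaccine. The documents do not support either. Day-missing stops outside the month of the last dose go to month end, and most post-prime durations become longer. Arm B events moved to the prime period add placebo-boost events to the BPZE1 prime total. Nor can one say that the persistent post-boost reaction would be reported as lasting 1 day: SAP 9.1 includes the diary days, so what follows is a conflict between 13.4 and 9.1.

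**Conclusion.** The concern holds in a limited form. Followed exactly, SAP 13.4 can place post-boost AEs in the prime period, give a stop date that contradicts the diary, and give two answers for one year-only stop date. The size is about 51% (day missing) and 96% (day and month missing) of partially dated post-boost AE starts moved to the prime period, under the uniform-date assumptions. The shift in duration differs by period and by type of partial date. The absolute effect cannot be stated, because the documents do not say how many dates will be partial. It should be corrected before the Day 113 database lock, so that period assignment is not settled after unblinding.

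A minor related point is missing severity. SAP 4.6 says it "will be imputed as related to study vaccine and severe, as the worst-case scenario", while SAP 9.2.2 says "If the severity is missing for one or more of the occurrences, the maximum severity of the remaining occurrences will be used". The second may be meant as a specific rule for repeat occurrences, but no precedence is given.

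**What to change.** For AEs only, leaving the prior and concomitant medication rules as they are:

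- **Start dates** (day missing, or day and month missing): if the partial date is compatible with one or more vaccinations and the stop date does not rule it out, impute the most recent compatible vaccination date, prime or boost.
- **Stop dates:** impute the latest possible date (month end or 31 December), capped at last contact and not earlier than the last diary day with the symptom. Delete the bullets that set a stop to a dosing date; this also removes the contradiction.
- **Severity:** state whether 4.6 or 9.2.2 takes precedence for repeat occurrences.

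The cost is appendix wording and a few lines of code. The downside is that some durations become longer, and some AEs that truly began before the boost will be assigned to the boost period.
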